Likewise platelet engraftment is delayed occurring at a median of 28 days (0-395 days) in patients undergoing haploidentical transplantation using T replete marrow graft with post-transplant cyclophosphamide.^[10] This is likely due to use of bone marrow as a graft source and use of cyclophosphamide after transplant, which results in significantly delayed engraftment. A major cause of mortality in these patients is infection resulting from poor immune reconstitution.^[2,7,14] Further effort at improving engraftment and immune reconstitution is clearly needed.

At MD Anderson Cancer Center, we have previously reported engraftment data in a smaller number of patients in both of these groups.^[15-18] In order to get detailed data for engraftment in a larger number of patients and to serve as a baseline for this proposal, we reviewed our historic platelet engraftment data in these two groups of patients and they are summarized in Table 2.

Table 2

	Cord blood (n=91)	Haploidentical Donor (n=54)
Time to platelet >20K Median (range) days	43 (0-126)	29 (0-59)
At Day 30 proportion of patients with		
Platelet >20K	19%	61%
Platelet >50K	2%	20%
At Day 60 proportion of patients with		
Platelet >20K	60%	88%
Platelet >50K	44%	63%

Hence at Day 30 after transplant only 2% (2/91) of patients receiving cord blood and only 20% (11/54) of patients receiving haploidentical graft achieved platelet count greater than 50,000/ μ l. We wish to improve these results in the current study.

Rationale for eligibility criteria and study design

We would like to include as many patients as possible therefore all patients receiving cord blood or haploidentical transplant treated on any protocol will be eligible for this study. Following exceptions are made for safety concerns.

- a) Patients with liver dysfunction are excluded from this study because the drug exposure is higher in patients with severe liver dysfunction and modest hepatic toxicity was observed in few patients in previous clinical trials of this drug. Likewise patients with renal dysfunction are excluded as limited data are available in the setting of kidney failure.

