4.0 Patient Eligibility

We would like to include as many patients as possible. Therefore, any patient receiving cord blood or haploidentical transplant treated on any protocol or as standard of care will be eligible for this study. Following exceptions are made for safety concerns.

- a) Patients with liver dysfunction are excluded from this study because the drug exposure is higher in patients with severe liver dysfunction and modest hepatic toxicity was observed in few patients in previous clinical trials of this drug. Likewise patients with renal dysfunction are excluded as limited data are available in the setting of kidney failure.
- b) East Asians (Chinese, Korean, and Japanese) have 87% higher drug exposure as determined by AUC than non-east Asians and therefore they may require a lower dose and a dose of 300mg may not be safe. Furthermore, at the most we are likely to see only one or at the most two patients if any of these ethnic groups during the course of this study, so doing a separate lower dose cohort for these groups is not realistic.

Hence, it will be safer to exclude them.

4.1 Inclusion Criteria:

1. Patients undergoing a cord blood or haploidentical transplantation on any protocol or standard of care treatment plan.
2. Age ≥ 18 .
3. Females of child bearing potential defined as not post-menopausal for 12 months or no previous surgical sterilization or breast- feeding must be willing to use an effective contraceptive measure until 30 days after the last dose of eltrombopag. Males who have had sexual contact with female of child-bearing potential must be willing to use contraceptive techniques until 30 days after the last dose of eltrombopag.
4. Patient or patient's legal representative(s) is/are able to provide written informed consent to participate.

4.2 Exclusion Criteria:

1. ALT and AST ≥ 2.5 ULN.
2. Serum direct bilirubin ≥ 1 mg/dl (except Gilbert's syndrome or hemolysis).
3. Patients of east Asian ancestry (Chinese, Japanese, or Korean Origin).
4. Calculated creatinine clearance < 30 ml./min. Creatinine clearance will be calculated using the MDRD method.
5. Arterial or venous thrombosis in the last year except for line-related venous thrombosis more than 3 months ago.
6. Positive beta HCG within 7 days prior to consent in female of child-bearing potential defined as not post-menopausal for 12 months or no previous surgical sterilization or breast-feeding.

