5.0 Treatment Plan

Dosage and Administration:

For inpatients: documentation of drug administration will be on the medication administration record (MAR).

For outpatients: patients will be given a pill diary to record dose taken, missed, or vomited.

Dose may be repeated if the patient vomits within 30 minutes of taking the drug.

1. Eltrombopag will be given as a single daily dose of 300mg orally on an empty stomach (1 hour before or 2 hours after a meal) for 60 total days.
2. Eltrombopag will be started on Day -1 (the day prior to stem cell infusion in cord blood patients) and Day +5 in patients receiving haploidentical transplant.
3. If for any reason patient is unable to take oral drug, number of days missed and reason will be documented.
4. Allow a 4-hour interval between eltrombopag and other oral medications/supplements containing polyvalent cations, such as iron, calcium, aluminum, magnesium, selenium, and zinc.
5. Drug will be stopped and not resumed:
 - a) if at any time platelet count is $\geq 250 \times 10^9/l$, or
 - b) after completing 60 days of treatment, or
 - c) at patient request, or
 - d) per PI discretion if patient misses more than 10 consecutive doses of drug,

or

- e) if it is deemed unsafe and detrimental to patient health by the treating physician or the principal investigator.

6. Patients will be taken off the study:
 - a) at patient request, or
 - b) if it is deemed unsafe and detrimental to patient health by the treating physician or the principal investigator based on CTCAE Version 4.0 toxicity grading, or
 - c) 1 year after drug initiated.

Unused and/or expired drug will be disposed per institutional policy.

Concomitant medications will be documented in the medical record but will not be entered into PDMS/CORE. These medications are considered standard of care and have no scientific contributions to the protocol, therefore no data will be captured on the various medications needed or their side effects.

The use of medications that cause thrombocytopenia is permitted if needed, at the discretion of the patient's physician.

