9.2 Causality Assessment

For the purpose of this study events known to be caused by Eltrombopag will be assessed as definitely related.

Events known to be caused by components of the transplant package and its direct consequences as well as those events known to be related to drugs used for the treatment of GVHD, infections and supportive treatment will be scored as unrelated. When the relationship of the adverse event cannot be ruled out with certainty the AE may be considered possibly related.

The PI will be responsible for assessing the causality and will be final arbiter. Documentation of grade, onset/resolution date and attribution will be entered into the patient's medical record and signed by the PI.

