9.3 Collection of adverse events

Only those events known to be caused by Eltrombopag will be recorded in the designated case report form (PDMS/CORE). Collection of adverse events will reflect the onset and resolution date and maximum grade. Intermittent events should be labeled as such and followed until resolution. If a patient is taken off study while an event still ongoing, this will be followed until resolution unless another therapy is initiated.

Events known to be caused by components of the transplant package and its direct consequences as well as those events known to be related to drugs used for the treatment of GVHD, infections and supportive treatment will not be collected in the designated case report form/database. Concurrent medications considered standard of care for transplant patients will not be captured in the case report form. They will be documented in the medical record.

Adverse events related to the study drug will be collected and recorded for the duration of active treatment plus 30 days.

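### Section 9.3, read with 9.2, leaves possibly related adverse events out of the case report form, so the toxicity summaries could understate drug-related toxicity

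*Combined protocol and SAP*

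**What the plan says.** Section 9.2 (Causality Assessment) sorts adverse events into three classes:

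- For the first class, "events known to be caused by Eltrombopag will be assessed as definitely related".
- Events known to come from the transplant package and its direct consequences, or from drugs for GVHD, infection or supportive care, are scored as unrelated.
- For the rest, "When the relationship of the adverse event cannot be ruled out with certainty the AE may be considered possibly related".

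The PI is the final arbiter.

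Section 9.3 (Collection of adverse events) opens with the case report form rule: "Only those events known to be caused by Eltrombopag will be recorded in the designated case report form (PDMS/CORE". Its second paragraph says of the transplant-caused group that these events "will not be collected in the designated case report form/database". It closes: "Adverse events related to the study drug will be collected and recorded for the duration of active treatment plus 30 days".

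Section 9.1 sends adverse events to PDMS/CORE without limiting them by attribution, and names that system as the electronic case report form. Section 8.0 (Secondary Endpoints) promises descriptive toxicity summaries by arm, and safety is the first secondary objective in 1.0. Section 9.6 sends every serious adverse event to the IND Office whatever its attribution.

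**The concern.** The limiting sentence in 9.3 uses the same phrase that 9.2 uses to define its definite class. A data manager who follows both sections would enter definitely related events and leave out possibly related ones. Another, relying on 9.1 or on the last sentence of 9.3, would enter both. The two toxicity tables would differ with no departure from the text by either person.

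The possible class need not be small. Patients have had conditioning and take several other drugs, and there is no concurrent control. A PI will often be unable either to establish or to exclude a role for eltrombopag. A summary limited to the definite class would then report only the events on which the PI was sure.

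**Working it through.** The plan states no figure on this point, so the check sets the texts side by side.

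**Step 1: what each text does with each class in 9.2.**

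| Class under 9.2 | 9.3, first sentence | 9.3, second paragraph | 9.3, last sentence | 9.1 |
|---|---|---|---|---|
| Definitely related | in | silent | in | in |
| Possibly related | out | silent | in, if related includes possibly related | in |
| Unrelated (known other cause) | out | out | out | in, if read literally |

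Within 9.3, the first and last sentences can disagree only on the middle row. The unrelated class is excluded throughout 9.3, which is a stated design choice. No text ranks the opening sentence against the closing one or against 9.1.

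**Step 2: where a possibly related event goes if it is left out.** If serious, it goes to the IND Office through the electronic SAE application (9.6). If not serious, it stays in the medical record, where 9.2 requires grade, dates and attribution. No text says that either source feeds the summaries in 8.0. I assume those summaries are drawn from PDMS/CORE, the only case report form named.

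**Step 3: direction and size.** Let D be the number of definitely related events and P the number of possibly related events. Under the opening sentence the summary shows D instead of D + P, a shortfall of P / (D + P). The documents give neither D nor P, so this share could lie anywhere from 0 to 1. If the definite and unrelated calls are correct, the number of events truly caused by the drug lies between D and D + P. The definite-only count is the lower end of that range and the fuller count the upper end.

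**Step 4: thrombosis.** Exclusion criterion 5 in 4.2 reads: "Arterial or venous thrombosis in the last year except for line-related venous thrombosis more than 3 months ago". The first expected harm in 9.4 is clots linked to thrombocytosis. The protocol therefore treats thrombosis as a risk of interest. The second paragraph of 9.3 bars only events *known* to have another cause. A clot of uncertain cause can be scored possibly related and falls under the main point. A clot that the PI confidently assigns to the transplant is left out by design.

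**The case against.** The strongest reply is that the restriction is deliberate and the rest of the text supplies the intent. The plan avoids filling its database with transplant complications, just as it does not capture concomitant medications. Section 9.1 and the end of 9.3 favour including possibly related events, and serious cases are reported whatever their cause. This stands in part: the intent may well be inclusive, and the serious cases are seen. But the reason for leaving out transplant complications does not extend to events in which the drug cannot be ruled out, and the sentence containing the word only is the most specific rule on the page.

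It can also be said that the opening phrase means event types known to be caused by the drug, such as those listed in 9.4. On that reading a possibly related event of an unlisted type would still be left out.

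Three stronger readings are tempting, and the documents do not support them:

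- **A weakened stopping rule.** A reader might infer that the grade 4 toxicity rule in 8.0 would miss events and stop too rarely. The plan does not say that the rule is counted from the case report form, or whether possibly related events count as drug-attributable. Any figure would also need an assumed share and would treat every possibly related event as truly caused by the drug. The change proposed here does not alter how that rule counts.
- **Line-related clots excluded.** Neither 9.2 nor 9.3 mentions the line, and the transplant package is not defined. Their exclusion is an inference. Stroke symptoms are listed in 9.4 in their own right, with no thrombocytosis condition.
- **Thrombocytosis-related clots uncommon on drug.** The historical platelet counts come from patients not given eltrombopag and use a 50K cut-off. They do not support a statement about treated patients.

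**Conclusion.** The point holds as a fault in the recording rule. Read with 9.2, the first sentence of 9.3 leaves possibly related events out of the case report form, while wider wording in 9.1 and at the end of 9.3 points the other way. The likely effect is that the summaries for secondary objective 1 understate drug-related toxicity. The amount cannot be estimated from the documents.

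The conclusion rests on two assumptions: that the 8.0 summaries are drawn from PDMS/CORE, and that the opening sentence of 9.3 is applied as written. Possibly related serious events remain visible to the IND Office, so the main loss is of non-serious events and of a complete toxicity dataset. The primary endpoint is unaffected. Severity is minor, and the change is a cheap improvement.

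**What to change.** In 9.3, replace the first sentence with: *Adverse events assessed under Section 9.2 as definitely or possibly related to eltrombopag are entered in the case report form (PDMS/CORE).* The second paragraph of 9.3, the list in 9.4 and the PI's role in attribution stay as they are.

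Optional: because thrombosis is both an exclusion criterion and the first expected harm, also record every arterial or venous thrombotic event, whatever its cause, from first dose to 30 days after the last dose, with the PI's attribution, and tabulate these events by arm. With 60 uninterrupted days of dosing, the window runs from Day -1 to Day 88 in the cord blood arm (last dose Day 58, plus 30) and from Day 5 to Day 94 in the haploidentical arm (last dose Day 64, plus 30). This adds description only. With no concurrent control and at most 60 patients, it cannot show that eltrombopag causes clots.

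The cost is one changed sentence, a few more entries and a higher reported toxicity rate, since some possibly related events will not be due to the drug. No new tests are needed, and 9.2 already requires grade, dates and attribution in the medical record. Carrying the attribution into each entry would let the summary show the two classes separately.

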9.4 List of expected adverse events related to Eltrombopag

1. Thrombotic episodes related to thrombocytosis.
2. Allergic reactions (rash; hives; itching; difficulty breathing; tightness in the chest; swelling of the mouth, face, lips, or tongue);
3. Abnormal liver function tests (possible liver damage-ascitis, jaundice).
4. New onset of bone marrow fibrosis.
5. Stroke symptoms (e.g., confusion, slurred speech, sudden vision changes, one-sided weakness).
6. Muscle aches or pain (arms and/or legs).
7. Bleeding problems after discontinuation of treatment.

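### Section 9.3 restricts the CRF to events known to be caused by eltrombopag, so non-serious liver abnormalities are probably under-recorded, and 8.0 plans no all-cause liver table to set beside them

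*Combined protocol and SAP*

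**What the plan says.** Section 9.3 opens with the recording rule: "Only those events known to be caused by Eltrombopag will be recorded in the designated case report form (PDMS/CORE". It then keeps out events known to come from the transplant package or from drugs for GVHD, infection or supportive care. It closes with a differently worded sentence: "Adverse events related to the study drug will be collected and recorded for the duration of active treatment plus 30 days".

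Section 9.2 sets three classes of attribution:
- **Definite:** "For the purpose of this study events known to be caused by Eltrombopag will be assessed as definitely related".
- **Unrelated:** events known to come from the transplant package, or from drugs for "GVHD, infections and supportive treatment will be scored as unrelated".
- **Possible:** "When the relationship of the adverse event cannot be ruled out with certainty the AE may be considered possibly related".

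On who decides, 9.2 says "The PI will be responsible for assessing the causality and will be final arbiter". On documentation it says "Documentation of grade, onset/resolution date and attribution will be entered into" the medical record, with the PI's signature.

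The expected drug effects in 9.4 include, as item 3, "Abnormal liver function tests (possible liver damage-ascitis, jaundice". Section 7.0 item 2 schedules bilirubin, alkaline phosphatase and ALT weekly on treatment and for 4 weeks afterwards. Section 8.0 promises a descriptive toxicity summary by arm and dose. It names no liver-test table.

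**The concern.** Safety is the first secondary objective, and hepatic toxicity is one of the reasons given in 4.0 for the exclusion criteria. After a transplant, a rise in ALT or bilirubin can come from eltrombopag, from conditioning, or from drugs given for GVHD or infection. All patients in both arms receive eltrombopag, so there is no concurrent control to separate these causes. The recorded rate then depends on how the PI attributes each event, and on whether the CRF accepts the doubtful ones. If it accepts only definite attributions, the safety summary omits the cases where the drug could not be ruled out, which are the ones a reader most needs to see. The liver tests that would give context are already scheduled, but no analysis of them is planned.

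**Working it through.** **1. Do possibly related events reach the CRF?** Compare the three classes in 9.2 with the three statements in 9.3.

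| Class in 9.2 | 9.3, opening rule | 9.3, exclusion | 9.3, last sentence |
|---|---|---|---|
| Definitely related | recorded | not excluded | recorded |
| Possibly related | not recorded | not excluded | unclear |
| Unrelated | not recorded | excluded | not recorded |

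The opening rule repeats the phrase that 9.2 ties to the definite class and begins with a restrictive word. The middle row is therefore out on a plain reading. The last sentence refers only to a relation to the study drug and could let that row back in. Two data managers could reasonably differ.

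**2. Direction.** Let d, p and u be the numbers of patients whose liver abnormality is classed definite, possible and unrelated (each patient counted once, in the strongest class). The strict CRF count is d, the lenient count is d + p, and the all-cause count is d + p + u. Since d ≤ d + p ≤ d + p + u, the strict rule can only lose cases in which the drug was not ruled out. The documents give none of d, p or u, so the loss p cannot be calculated.

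**3. What is protected.** Section 9.6 sends all SAEs to the IND Office whatever their attribution. The gap is therefore in non-serious events.

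**4. The plan's own attribution-dependent figure.** This is the early stopping table in 8.0. An exact recursion with the Beta(0.4, 1.6) prior, stopping when Pr(rate > 0.20) > 0.95, a check after each patient and a maximum of 55 (a stop at patient 55 not counted as early) gives 0.003, 0.017, 0.063, 0.188, 0.425, 0.696, 0.887 and 0.971. All eight stated values reproduce.

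The following is an illustration on assumed attribution rates, for grade 4 or higher events only. It does not measure the gap above.
- If the true rate is 30% and half the events are attributed, the counted rate is 0.30 × 0.5 = 0.15, and early stopping falls from 0.696 to 0.063.
- If the drug rate is 10% and an independent 20% background is also attributed, the counted rate is 1 − 0.90 × 0.80 = 0.28, and early stopping rises from 0.017 to 0.592.

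The rule is sensitive to what counts as attributable, so 8.0 should say how possibly related events are treated.

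**5. Precision of an all-cause table (assumed counts, Clopper-Pearson).** With 3 events in 55 haploidentical patients, 3/55 = 5.5%, 95% CI 1.1% to 15.1%. If that arm fills, 60 − 55 = 5 cord blood patients remain. With 0/5 the upper limit is 1 − 0.025^(1/5) = 52.2%, so that arm is descriptive only.

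**6. Data burden.** Weekly panels: (60 + 30)/7 = 12.9 per patient, and 60 × 90/7 = 771 in all. Entering only the pre-dose and worst values: 60 patients × 3 tests × 2 values = 360.

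**The case against.** The strongest reply is that the text is more complete than it looks. Section 9.2 provides for doubtful causation. The exclusion in 9.3 covers only events known to have other causes, and its last sentence collects drug-related events. The toxicity summary in 8.0 carries no attribution limit, and 9.1 enters protocol specific data in PDMS/CORe, so a liver table could be built later. The medical record holds grade and attribution. An all-cause table cannot isolate the drug effect without a control, and the historical data in Table 2 contain no liver rates.

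Most of this stands, and it limits the point to a minor one. It does not remove the restrictive opening rule in 9.3. A table that could be built later leaves the choice of tests, window and baseline open until the results are known.

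A reader might infer three stronger things that the documents do not support:
- *That liver events will also be over-recorded.* This requires reading the definite class in 9.2 as a type of event, so that anything on the 9.4 list counts as definite. Read as a judgement on each event, nothing forces a transplant-related rise onto the drug.
- *That the ITP figures in 3.0 (10% on eltrombopag, 7% on placebo) give the size of the error.* The same sentence says such abnormalities were infrequent in HCV and chemotherapy studies. Section 3.0 also cites four studies reporting safety at 300 mg, one of them in transplantation. No transplant background rate is given.
- *That the Day 60 rule is invalid.* Its operating characteristics reproduce, and 8.0 does not say that its events come only from the CRF.

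**Conclusion.** The point holds as a minor one. As written, 9.3 leaves possibly related events out of the CRF, with some ambiguity. The recorded rate of non-serious liver abnormalities therefore depends on PI judgement and most likely falls short of the cases in which the drug could not be excluded. This rests on giving the opening rule of 9.3 its plain meaning and on the PI using the possibly related class at all. The size is unknown, because the documents give neither the frequency of such events nor a transplant background rate. The effect is confined to the descriptive safety summary. No primary test, sample size or stopping boundary changes.

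**What to change.** 1. **Section 9.3.** Replace the opening rule with: *Events definitely or possibly related to eltrombopag will be recorded, with the attribution.*
2. **Section 8.0, toxicity summary.** Tabulate by arm, for all treated patients and whatever the attribution, the worst CTCAE v4.0 grade of ALT, bilirubin and alkaline phosphatase from first dose to 30 days after last dose. Set it against the last available pre-dose value where one exists, with its date. Give the proportion with grade 3 or higher with an exact 95% CI, beside the attributed summary, and label the table all-cause and descriptive.
3. **Section 9.1.** Name the pre-dose and worst values of these tests as protocol specific data.
4. **Section 8.0, monitoring rule.** State whether possibly related events of grade 4 or higher count as attributable. The boundaries stay as they are.

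The date in item 2 matters because haploidentical patients start on Day +5, so the last pre-dose value may precede conditioning and the shift may include conditioning effects. A pre-dose alkaline phosphatase may be missing: 4.2 calls only for ALT, AST and direct bilirubin, and 6.0 refers only to the standard work-up.

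**Cost.** About 360 values to enter. If they are not already in PDMS/CORe, up to about 771 weekly panels must be read to find them. Patients already enrolled need a record review for possibly related events. No on-study tests are added. The all-cause rate will include transplant and GVHD-related abnormalities, will look less favourable, and cannot isolate the drug effect. It is not a strict upper limit either, since AST is not named in 7.0 and clinical liver events are not in the table.
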